During the recruitment telephone call, interested individuals will be asked questions to confirm eligibility, to determine their access to and facility with technological devices, and the extent to which they can access broadband internet. Should the participant need a device to participate in the visits described in this protocol, the study team will send a device with Wi-Fi and cellular data capabilities for participants' temporary use. Eligible participants will be consented orally, assigned Outcome Measure surveys, and then assigned to a study arm (*see randomization section below*). Participants assigned to the Intervention arm will be scheduled additional visits with a Pain Care Manager (PCM) and Community Health Worker (CHW). Interested individuals will not be assigned to an arm until their Outcome Measure surveys are completed. This same Outcome Measure survey bundle will be assigned to enrolled participants either on paper or electronically at 3 months and 6 months post enrollment. Enrolled participants will be mailed a copy of the oral consent so the discussed details and team contact information is readily available to them.

We are seeking a waiver of signed informed consent as well as a waiver of signed HIPAA for this protocol. Due to the minimal risk posed by this study, as well as the complexities of recruiting rural and Hispanic populations and the likelihood of including undocumented Hispanic participants, we believe that a waiver is justified and consistent with the intent of existing regulations.

Randomization

This will be a two-arm, parallel group randomized clinical trial. Research coordinators will register participants

on a password protected MC Cancer Center remote registration/randomization application. Randomization will use a dynamic allocation procedure that balances the marginal distributions of the stratification factors per Pocock-Simon randomization method.¹ Stratification factors will include cancer stage, rural residence, MC HCS site, and Hispanic ethnicity.

The participants randomized into the control group will receive enhanced usual care which will include access to the educational and pain self-management materials developed for the ASCENT trial. Those randomized into the intervention will follow the process outlined in the “Intervention” section of this protocol.

Remuneration

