IVR will be utilized to supplement the collection of PROMs. These PROMs will include the pain assessments used to tailor and individualize the ASCENT intervention, as well as the ASCENT trial outcomes. Trial primary and secondary outcomes will be collected at 3- and 6-months from the patients who do not complete them via Epic Welcome tablet or patient portal. The RevSpring platform will be used to collect IVR data. The IVR data will be maintained on password-protected secure Mayo Clinic servers within the firewall. No PHI data will be released to RevSpring. RevSpring has been used by the Mayo Clinic Spine Center to securely administer follow-up PROMs to over two thousand patients. Data going to the RevSpring platform is transient in nature and is purged once the results are uploaded into Epic. TAP approval has been granted to RevSpring's IVR system and there are Business Associate Agreements (BAA) and Information Security Agreements (ISA) in place, which covers how PHI can be used and stored. The ASCENT pain NRS questionnaire responses will reside on our server and will not go outside of the firewall. Additionally, RevSpring is providing the platform for the texting

capabilities, mentioned in the “follow up touchpoints” section. Study team members will only text study participants and participants will be asked to “opt in” to start receiving the messages.

ASCENT Trial Outcomes

Trial outcomes will include PROMs, healthcare utilization, and employment status. NIH Helping to End Addiction Long-term (HEAL) Initiative Clinical Pain Common Data Elements will be used if validated Spanish translations are available excepting QoL, for which no HEAL measure has been specified. PROMs, **Table 2**, will be administered at baseline by a study coordinator and at 3 and 6 months by a blinded, bilingual, assessor. Valid Spanish translations are available for all PROMs.

Primary outcome The Brief Pain Inventory SF (BPI SF), has been used among diverse populations.⁷⁻⁹ Its psychometric performance characteristics have proven excellent and robust in diverse types and stages of cancer.^{10,11} The BPI SF has been used in disparity-focused trials among Hispanic persons.¹² A Spanish version has been widely used for almost two decades.¹³

Secondary outcomes Will include physical function (PROMIS Physical Functioning SF 6b), quality of life (EQ5D-3L),¹⁴ depression (PHQ-2), anxiety (GAD-2), sleep (PROMIS Sleep Disturbance 6a), and self-reported employment status.

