Mediators Will include self-efficacy for managing symptoms (PROMIS SF 4a), adherence to behavioral MMPC plan components (logged count data), use of ASCENT e-tools (minutes/week), social isolation (PROMIS SF 4a), informational support (PROMIS SF 4a), and opioid consumption in oral morphine equivalents (OMEs) collected via EHR prescriptions.

Health care utilization Healthcare utilization for ASCENT will consider hospitalizations and ED visits which will be ascertained using EHR entries and administrative billing data. Data collected for hospitalizations will include admission and discharge diagnoses, length of stay, whether an admission was planned for anti-cancer treatment or unplanned. The majority, but not all, of patients’ health care utilization will occur at MC facilities. Established patterns suggest that 80% of patients care will occur at an MC facility. However, we will use imputation methods and sensitivity analyses to assess the impact of mis-ascertainment of utilization data.

Measure	Domain	Items	Time min.	HEAL data	Collected 0,3,6 mo.
Primary					
BPI SF	Pain	7	3	✓	✓
Secondary					
PROMIS SF	Physical Function	4	2	✓	✓
EQ-5D-3L	QoL	5	2.5		✓
PHQ-2	Depression	2	2	✓	✓
GAD-2	Anxiety	2	1	✓	✓
PROMIS SF	Sleep	6	3	✓	✓
Mediators					
PROMIS SF	Self-efficacy	4	2		✓
PROMIS SF	Social isolation	4	2		✓
PROMIS SF	Informational support	4	2		✓

Risks and Benefits

The risks of the ASCENT trial study are minimal as participants are being potentially offered additional support and expertise to manage pain. Nothing in this trial will impede patients them from receiving whatever pain

treatment they and their team agree are appropriate and evidence-based. The benefits to patients include the potential for safer and more guideline-concordant pain management and lower risk of opioid exposure and dependency.

Protection of Human Subjects

Care will be taken to ensure that patients' data are protected. Data from chart review, patient-reported preferences, and patient-reported outcomes will be stored securely on password protected Mayo Clinic research servers within the firewall. Clinicians will still be able to make professional judgments about the appropriateness of engaging patients in specific conversations about pain management throughout their post-surgical recovery and may disregard EHR-prompts as appropriate.

Subject Information

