Target accrual is the proposed total number of subjects to be included in this study at Mayo Clinic. A "Subject" may include medical records, images, or specimens generated at Mayo Clinic and/or received from external sources.

Target accrual: Up to 660

Subject population (children, adults, groups): Adults

Inclusion Criteria:

- A qualifying liquid or solid cancer diagnosis with visits at a participating Mayo site in the past 15 years
 - Including malignant hematology
 - Lymphoma
 - Myeloma
 - Chronic Leukemias
- Age ≥ 18
- NRS pain score of $\geq 5/10$
- Pain that developed or worsened following cancer diagnosis.
- Fit the description of either rural or Hispanic or both.

Exclusion Criteria:

- PHQ8 score of ≥ 13 .
- Hospice enrollment
- Skilled nursing facility, inpatient rehabilitation facility, or long-term care placement
- Encounters with Palliative Care or the Pain Clinic in the past two months or upcoming two months
- Any mention of hospice referral in medical oncology encounter notes (assess through textual search of the Mayo Data Explorer)
- Affirmative response to, "Are you usually confined to a bed or chair more than a third of your waking hours because of your health?"
- Currently homeless.
- Do not feel safe in their home.

- New or worsening chest pain, chest tightness, or chest pressure.
- Back pain that is associated with a new or worsening weakness, control of bowels/bladder, or difficulty walking.
- Lightheadedness, inability to keep down food or fluids, or vomiting blood or dark coffee-grounds-like material.
- New or worsening headaches that are associated with vision changes, nausea, balance issues, or problems with speech.
- Screens positive for use of non-cannabis drug use at a frequency of monthly or greater
- Inability to engage with the intervention due to medical or psychological reasons

Review of medical records, images, specimens

Check all that apply (data includes medical records, images, specimens).

Only data that exists before the IRB submission date will be collected.

Date Range for Specimens and/or Review of Medical Records:

Examples: 01/01/1999 through 12/31/2015, or all records through mm/dd/yyyy.

Note: The Date Range must include the period for collection of baseline data, as well as follow-up data, if applicable.

The study involves data that exist at the time of IRB submission **and** data that will be generated after IRB submission. Include this activity in the Methods section.

Examples

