- The study plans to conduct a retrospective chart review and ask subjects to complete a questionnaire.
- The study plans to include subjects previously diagnosed with a specific disease and add newly diagnosed subjects in the future.

The study will use data that have been collected under another IRB protocol. Include in the Methods section and enter the IRB number from which the research material will be obtained. *When appropriate, note when subjects have provided consent for future use of their data and/or specimens as described in this protocol.*

Enter one IRB number per line, add more lines as needed

Data Specimens Data & Specimens _____

Data Specimens Data & Specimens _____

Data Specimens Data & Specimens _____

Data Analysis

All methods will be appropriate for a patient-randomized, multi-site study. In addition, because our primary aim is to assess effectiveness in two potentially overlapping subgroups, we will use a Sidak corrected alpha of $\alpha = 0.0253^{15}$ to assess significance. We will summarize patient characteristics by study arm, and report standardized mean differences (SMDs) to assess balance; we will do this for the entire cohort as well as separately for Hispanic and rural patients. Then, to assess the effectiveness of the intervention on the primary and secondary outcomes we will estimate a series of generalized linear models, each estimated separately for Hispanic and rural patients, respectively, with outcome as dependent variable and intervention status indicator. Each model will be specified with a link and distribution appropriate for the outcome, e.g., logit or linear, and include indicators for randomization factors and any characteristics that have $SMD > 0.1$ across groups. By testing whether the coefficient of the intervention status differs from zero we can assess whether the intervention has an impact on the outcome.

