All variables will be assessed to ensure that distributional assumptions are met and, if not, different strategies considered, including transformations, categorization, and revised model specifications. For outcomes which are collected multiple times we will include random latent effects (mixed effects models) for each patient. All models will be assessed for goodness of fit using methods appropriate for the specification, including C-statistics, R^2 values, and residual plots. All variables will be assessed for missingness; patterns of missingness will be examined and if appropriate multiple imputation used to account for missing values in model estimation.

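### Covariates in the primary models are picked by observed imbalance (SMD > 0.1), so baseline BPI, collected before randomisation, is not assured a place in either model

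*Protocol*

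**What the plan says.** The Data Analysis section of the protocol fits separate models for Hispanic and rural patients and gives one covariate rule for all of them: they will "include indicators for randomization factors and any characteristics that have $SMD > 0.1$ across groups". SMDs are computed at several levels: "we will do this for the entire cohort as well as separately for Hispanic and rural patients". The text does not say which of these triggers entry.

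The randomisation factors are listed under Randomization: "Stratification factors will include cancer stage, rural residence, MC HCS site, and Hispanic ethnicity". No measure of baseline pain is among them.

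Baseline BPI is nevertheless available for everyone before allocation. Under Consenting: "Interested individuals will not be assigned to an arm until their Outcome Measure surveys are completed". Table 2 under ASCENT Trial Outcomes heads its schedule column "Collected 0,3,6 mo", and BPI SF is ticked in it.

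On repeated measures, Data Analysis adds: "For outcomes which are collected multiple times we will include random latent effects (mixed effects models) for each patient". It does not say whether the month 0 value is a covariate, a response or unused, and it describes no time term.

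**The concern.** The rule selects covariates by how far they happen to differ between arms, not by how well they predict the outcome. In a randomised trial any baseline difference is due to chance. What makes a covariate worth including is its correlation with the outcome, and the baseline value of the outcome itself is usually an obvious candidate.

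If the baseline BPI counts as a characteristic, it enters only in trials where chance imbalance passes 0.1 SD. If it does not, the stated rule never brings it in. Either way the content of the primary model is unknown until baseline data have been compared by arm, and the Hispanic and rural models may end up with different covariates. At stake is a wider interval than the collected data allow, and lower power if the true effect is smaller than planned.

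**Working it through.** **The plan's own figures.** Sidak alpha: 1 − 0.95^0.5 = 0.0253, two-sided critical value z = 2.237. Per arm for 0.40 SD and 90% power: 2 × (2.237 + 1.282)² / 0.40² = 154.8, so 155 by the normal formula; the t-test version gives 155.99, so 156 as stated. Total: 312 × 1.9 / 0.9 = 658.7, so 659, with 593 followed up. The sample size reproduces, and it takes no credit for baseline adjustment.

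**Chance that baseline BPI enters.** Under randomisation the SMD has standard error √(2/n) with n per arm, so P(|SMD| > 0.1) = 2 × [1 − Φ(0.1/√(2/n))].

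- Subgroup, completers: n = 312/2 = 156 gives 0.377.
- Subgroup, enrolled: n = 312/0.9/2 = 173 gives 0.352.
- Whole cohort, completers: n = 593/2 = 296 gives 0.224.
- Whole cohort, enrolled: n = 659/2 = 330 gives 0.199.

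If the SMD is judged within each subgroup, and the subgroups are treated as independent (they overlap slightly), the two primary models differ in carrying baseline BPI in 2 × 0.377 × 0.623 = 47% of trials (46% on enrolled numbers). If it is judged in the whole cohort, they never differ.

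**Precision and power.** Assumptions: 156 completers per arm, outcome rows at months 3 and 6, equal SDs, and one common correlation ρ among months 0, 3 and 6. The protocol gives no value for ρ, so a range is shown. In units of the single-visit variance, the month 3/6 mean has variance (1+ρ)/2 without baseline and (1+ρ)/2 − ρ² with it. The interval ratio is the square root of their quotient. Closed-form power is Φ(effect/√(2 × variance/156) − 2.237). The rows for the rule come from simulation: a t test without baseline, or ANCOVA when |SMD| > 0.1. There were 200,000 trials per setting for type I error and for 0.30 SD, and 60,000 for 0.40 SD. The whole-cohort version adds 296 − 156 = 140 other patients per arm to the SMD.

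| | ρ = 0.2 | 0.3 | 0.5 | 0.7 |
|---|---|---|---|---|
| Variance, baseline out | 0.60 | 0.65 | 0.75 | 0.85 |
| Variance, baseline in | 0.56 | 0.56 | 0.50 | 0.36 |
| Interval ratio, out/in | 1.035 | 1.077 | 1.225 | 1.537 |
| Type I error, rule, subgroup SMD (nominal 2.53%) | 2.3% | 2.1% | 1.5% | 1.1% |
| Type I error, rule, whole-cohort SMD | 2.4% | 2.3% | 2.0% | 1.6% |
| Power at 0.30 SD, always in | 90% | 90% | 93% | 98% |
| Power at 0.30 SD, rule, subgroup SMD | 89% | 88% | 87% | 87% |
| Power at 0.30 SD, rule, whole-cohort SMD | 89% | 86% | 83% | 81% |
| Power at 0.30 SD, never in | 88% | 85% | 79% | 74% |
| Power at 0.40 SD, rule, whole-cohort SMD | 99% | 99% | 98% | 97% |
| Power at 0.40 SD, never in | 99% | 98% | 97% | 94% |

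At 0.40 SD the rule with subgroup SMD gives about 99% throughout, and baseline always in gives 99.3% to above 99.9%.

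**Range-restricted case.** The NRS entry threshold of 5 may weaken the link between baseline and follow-up. With 0.33 between baseline and follow-up and 0.5 between months 3 and 6, the variances are 0.75 and 0.75 − 0.33² = 0.641, so the ratio is 1.082. Type I error under the rule is 2.0% (subgroup) or 2.3% (whole cohort). Power at 0.30 SD is 82% or 81%, against 85% always in.

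**One follow-up visit instead of two.** Here adjustment multiplies the SD by √(1 − ρ²). At 0.40 SD and 156 per arm, power is 90.2% unadjusted. With 40,000 simulated trials per setting at ρ = 0.3 / 0.5 / 0.7, the rule with subgroup SMD gives 91.3 / 93.8 / 96.5%, against 92.4 / 96.6 / 99.6% with baseline always in. Type I error under the rule is 2.4 / 1.8 / 1.3%.

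**The case against.** Four points can be made for the plan.

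- **Naming the baseline outcome as a covariate is often left to the SAP**, and the sentence says what the models include without saying that nothing else may enter. That is true, and an SAP could add baseline BPI without contradicting it. But the protocol does not stay silent: it states a selection rule, and that rule does not secure baseline BPI.
- **The mixed-model sentence could be read as already using baseline.** If month 0 were a response row, the intervention indicator were coded zero before allocation, and time effects were fitted, the efficiency would be close to ANCOVA. The protocol states neither that coding nor any time term, so this is a possible reading and not a safeguard.
- **The consequence is small at the design effect.** At 0.40 SD with two follow-up visits, power under the rule is about 97 to 99%. The larger power gaps need a true effect nearer 0.30 SD. This stands.
- **The larger figures need correlations of 0.5 to 0.7, which the protocol does not support.** At 0.2 to 0.3 the widening is 4 to 8%, and the rule costs about 1 to 4 points of power at 0.30 SD. The widening also describes trials where baseline is left out, not an average over trials. The simulations omit the randomisation factors and other baseline PROMs that might share variance with BPI. This also stands, and the low-correlation columns should be read first.

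**Conclusion.** The point holds as a free improvement. As written, baseline BPI is left out of a given primary model in about 62% of trials (subgroup SMD) or 78% (whole-cohort SMD), or in all of them if it is not a characteristic. Where it is left out, the interval is wider by 4 to 8% at correlations of 0.2 to 0.3, and by 22 to 54% at 0.5 to 0.7.

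The test under the rule is conservative. When baseline is left out because the arms are well balanced on it, the unadjusted difference varies less than its standard error assumes. There is no bias and no inflated error, and the sample size stands. These sizes rest on the assumed correlations and on months 3 and 6 as the outcome rows. The reading of the covariate rule does not depend on either.

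**What to change.** In Data Analysis, state that baseline BPI is a covariate in both the Hispanic and the rural primary model whatever its SMD, alongside the randomisation factors, and that each repeated secondary PROM is adjusted for its own baseline value in the same way. Settle this before baseline data are compared by arm.

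As a clarification, state that the outcome rows are months 3 and 6. This fits the Data Collection wording on the IVR back-up: "Trial primary and secondary outcomes will be collected at 3- and 6-months". The protocol does not call for pooling month 0 as a response, but if that were done under a single intervention coefficient, 0.40 SD would become 0.40 × 2/3 = 0.267 SD.

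If the SMD rule is kept for other characteristics, say which population's SMD triggers entry, or confine the rule to a sensitivity analysis.

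The cost is one or two sentences for the main change, with no new data and no new patients.

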C.9.viii. Sample size. Our sample size is determined by the number of patients needed to detect a standardized effect of 0.40 between intervention groups, within either the Hispanic or rural subgroup of patients. The choice of 0.40 SD was informed by the 11-point NRS pain score, which we expect to closely align with the BPI. In preliminary analyses using data from the ongoing E2C2 study,²⁰⁻²² we found the standard deviation for the NRS pain score to be 2.7 for Hispanic cancer patients and 2.5 for rural dwelling cancer patients. Thus 0.40 SD corresponds to approximately a 1 point difference in the NRS pain score; 0.40 also conventionally corresponds to a 'medium' effect size.²³ Notably, a 1-point difference on the BPI as well as other 0 to 11 pain NRS has been shown to be a clinically important difference.^{24,25} The sample size needed to detect a standardized effect of 0.40

with a power of $1-b = 90\%$ and an $a = 0.0253$ (Sidak adjusted for 2 comparisons) is 156 per arm or 312 per group. We anticipate that approximately 10% participants will be rural dwelling Hispanics, based on the fact that ~90% of Hispanic cancer survivors treated at the Mayo Clinic Comprehensive Cancer Center are urban dwelling, RUCA 1 and 2, so assume approximately 10% overlap between the two groups. Allowing for a 10% loss to followup, we therefore plan to enroll $312 \times 1.9/(90\% \text{ followup}) = 659$ patients, of whom at least 50% are Hispanic and 50% rural dwelling.. For other outcomes, we assume followup on 593 patients and will have 90% power to detect a smaller standardized effect of 0.3 with an uncorrected $a = 0.05$. The exploratory subaim will be used to generate hypotheses for further work; results will be descriptive, with confidence intervals reported as appropriate.

References

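### The protocol tests one intervention coefficient for a BPI collected at 0, 3 and 6 months, names no primary time point and does not keep the pre-randomisation score out of the response

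*Protocol*

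**What the plan says.** Under ASCENT Trial Outcomes, the BPI SF is the primary outcome. The PROMs "will be administered at baseline by a study coordinator and at 3 and 6 months", and the outcome table marks the BPI for collection at 0, 3 and 6 months. The Consenting section places month 0 before randomisation: "Interested individuals will not be assigned to an arm until their Outcome Measure surveys are completed".

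Data Analysis sets out generalized linear models, fitted separately in Hispanic and rural patients, with the outcome as dependent variable and an intervention indicator. The covariates are the randomisation factors and any characteristic with a standardized mean difference above 0.1. The test is of one parameter: "By testing whether the coefficient of the intervention status differs from zero we can assess whether the intervention has an impact on the outcome". The rule for repeated measures is: "For outcomes which are collected multiple times we will include random latent effects (mixed effects models) for each patient".

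The Sample size section plans to "detect a standardized effect of 0.40 between intervention groups, within either the Hispanic or rural subgroup of patients", with 90% power at alpha 0.0253, and concludes: "Sidak adjusted for 2 comparisons) is 156 per arm or 312 per group". No visit is attached to the 0.40.

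**The concern.** Two things are left open that together define the primary result.

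The first is when the effect is judged. Neither the analysis nor the sample size says whether the claim concerns month 3, month 6 or an average of the two.

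The second is the role of the month-0 score. The BPI is an outcome collected more than once, month 0 is one of those occasions, and the random-effects rule excludes no visit. The baseline BPI is not named as a covariate either; it would enter only if it happened to be imbalanced. An analyst following the text could therefore stack all three scores as responses and test the single arm coefficient. Arms are assigned after month 0, so the true difference there is zero, and the coefficient would average that zero with the follow-up differences. The reported benefit would be too small, and the power would not be the power that was planned.

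**Working it through.** **Inputs from the protocol.** Effect 0.40 SD, alpha 0.0253, power 90% and 156 per arm (Sample size); loss to follow-up 10% (same section); BPI at 0, 3 and 6 months (ASCENT Trial Outcomes). The test is taken as two-sided, which the protocol does not state; a one-sided test would need only 131 per arm, so two-sided is what matches. The two-sided critical value is 2.237.

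**Assumptions, not in the protocol.** Equal SD at all visits, one common within-patient correlation r, and a 0.40 SD effect at both month 3 and month 6.

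**1. The stated design.** SE = √(2/156) = 0.1132 SD. Power = Φ(0.40/0.1132 − 2.237) = Φ(1.296) = 90.2%. A two-sample t-test calculation gives 155.99, so 156 per arm. The plan's figure reproduces as a comparison at a single time point.

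**2. Month 0 included as a response, one arm coefficient.** With balanced visits and a random intercept, the coefficient is the difference in patient means:

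- expected value = (0 + 0.40 + 0.40)/3 = 0.267 SD, one third below 0.40
- SE = √(2 × [(1 + 2r)/3] / 156)

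**3. Months 3 and 6 only.** Expected value 0.40 SD; SE = √(2 × [(1 + r)/2] / 156).

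| r | SE, three visits | Power, three visits | SE, months 3 and 6 | Power, months 3 and 6 |
|---|---|---|---|---|
| 0.3 | 0.0827 | 83.8% | 0.0913 | 98.4% |
| 0.5 | 0.0925 | 74.1% | 0.0981 | 96.7% |
| 0.7 | 0.1013 | 65.4% | 0.1044 | 94.5% |

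**4. Where the loss of power starts.** The three-visit analysis matches the stated design when (2/3)/√((1 + 2r)/3) = 1. That gives (1 + 2r)/3 = 4/9, so r = 1/6, about 0.17. Below that value averaging three visits gains more precision than the dilution costs: at r = 0.1 power is 93.1%.

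**5. Narrower baseline spread.** Entry requires a pain score of at least 5, which may shrink the month-0 SD. If it is k times the later SD, the variance factor is (k² + 2 + 2r(2k + 1))/9. With k = 0.6 (assumed) this is 0.409, 0.507 and 0.604 at r = 0.3, 0.5 and 0.7, and power is 92.6%, 85.8% and 78.6%.

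**6. Dropouts who contribute only month 0.** Take 173 per arm, of whom 17 (10%) have only the month-0 score. Information per arm is I = 156 × 3/(1 + 2r) + 17, and the expected coefficient is [156 × 0.80/(1 + 2r)]/I. At r = 0.5 this is 62.4/251 = 0.249 SD. Over r = 0.3, 0.5 and 0.7 the coefficient is 0.252, 0.249 and 0.245 SD, a dilution of 37% to 39%, with power 81.5%, 70.8% and 61.4%. One third is therefore not an upper limit.

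**The case against.** The strongest reply is that no sentence makes month 0 a response. The outcome table says when the instrument is administered, not what enters the model. Two follow-up visits are enough to trigger the random-effects rule. One sentence in ASCENT Trial Outcomes speaks of collecting primary and secondary outcomes at 3 and 6 months, and pre-randomisation characteristics appear elsewhere in the analysis as covariates. Visit terms and baseline handling are also often left to a statistical analysis plan, and none is at hand here. Finally, an average over 3 and 6 months is a legitimate target and has more power than month 6 alone.

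Much of this stands. A reader might infer that the primary test includes month 0, that the effect estimate is biased toward zero, and that the 90% power is lost. The document does not support that as fact. Inclusion of month 0 is a reading the text permits, not one it states. The power loss also needs a within-patient correlation above about 0.17 with equal SDs, and a higher one if the baseline spread is narrower. Nor does the document support the view that only a 6-month contrast would be right.

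Two parts do not stand. The sentence about 3 and 6 months describes back-up collection by interactive voice response; it does not define the model's response. And this is more than detail deferred to a later plan: the protocol itself states the model and the tested parameter, and fixes that parameter in a form that leaves its meaning open. The time at which the primary outcome is judged belongs in the protocol.

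**Conclusion.** The point holds as an ambiguity in the primary analysis that should be fixed; bias is not demonstrated. It is certain from the text that one coefficient is tested, that no primary time point is named in the analysis or the sample size, and that the month-0 score is not kept out of the response.

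The size depends on the reading. With month 0 as a response, the dilution is one third (0.27 instead of 0.40 SD) given equal effects at both follow-up visits and complete data, and somewhat more if dropouts contribute only month 0. The protocol equates 0.40 SD with about 1 point on the pain scale, so a true 1-point benefit would be reported as about 0.67 point. Power would be roughly 84% to 65% for correlations of 0.3 to 0.7 with equal SDs, and higher if the entry cut-off narrows the baseline SD. With months 3 and 6 as the only responses, month 0 dilutes nothing and power exceeds the planned 90% over the same range. The correlations, the SD ratio and the equal effect at both visits are assumptions; the protocol gives none of them.

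**What to change.** In Data Analysis:

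- State that only the 3- and 6-month BPI values are responses in the primary model, with baseline BPI as a covariate. Alternatively, keep month 0 as a response with the arm means constrained equal there.
- Include visit and arm-by-visit terms.
- Name one primary contrast in advance, either the 6-month difference or the 3/6-month average, and test it at 0.0253 in each subgroup. The choice is the sponsor's. Under the assumptions above, without baseline adjustment, the 6-month difference has 90.2% power and the average about 95-98%; the former answers whether pain is better at the end of follow-up.
- State in the Sample size section which contrast the 0.40 SD refers to.
- Handle the repeatedly measured secondary outcomes in the same way.

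The cost is wording in the protocol and in any statistical analysis plan. No new data or patients are needed, but the contrast must be fixed before outcome data are examined by arm.
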